10.6 OPERATIVE PROCEDURES

The investigator should use his or her standard, small-incision, cataract extraction surgical technique. Lenses should be folded for implantation and inserted into the capsular bag using one of the AMO-validated insertion systems described in Section 7.2.

Investigators should manage surgical outcomes to ensure that the total postoperative refractive astigmatism is as minimal as possible. The total postoperative astigmatism, including surgically-induced astigmatism, should be targeted to be no greater than 1.0 D. Astigmatism may be managed by incision type and placement only. **No additional refractive procedures are to be performed during the operative procedure or throughout the postoperative study period (e.g., LRI, OCCI, CRI, AK, PRK, LASIK or LASEK).**

Operative case report forms will include the following information:

INCISION TYPE AND SIZE

Lenses should be inserted through an incision ranging in size from approximately 2.2-3.0 mm, per the investigator's standard technique when using the UNFOLDER Platinum 1 Series Implantation System or the ONE SERIES Ultra Implantation System. The incision may be clear corneal, limbal or scleral tunnel at the discretion of the investigator.

CAPSULORHEXIS SIZE AND METHOD

The anterior capsulotomy should be a continuous, curvilinear capsulorhexis approximately 5.0 to 5.5 mm in diameter to allow slight overlap of the lens optic edge. The anterior capsulotomy method may be manual (rhexis) or laser-assisted.

LENS REMOVAL

Lens removal may occur using laser fragmentation combined with phacoemulsification/aspiration or using only phacoemulsification/aspiration.

VISCOELASTIC

Viscoelastic materials should be used as is customary for each investigator and recorded on the case report form (CRF).

IMPLANT INSTRUMENTATION USED

Lenses should be folded for implantation and inserted into the capsular bag using either the UNFOLDER Platinum 1 Series Implantation System (DK7796 handpiece with the Platinum 1 Series cartridge, Model 1MTEC30) or the ONE SERIES Ultra Implantation System (DK7786 [plunger] or the DK7791 [twist] handpieces with the ONE SERIES Ultra cartridge, Model 1VIPR30).

SURGICAL COMPLICATIONS

Should a surgical complication occur, implantation of a study lens will be at the investigator's discretion. In the event of capsular bag or zonular rupture, the lens should not be implanted if the complication may result in lens instability. Additionally, the lens is

not to be implanted in the sulcus. In this case, the investigator may implant his/her choice of a back-up, non-investigational IOL. The subject should be exited from the study if a non-study lens is implanted as a result of a surgical complication during the first-eye implantation; however, the eye will be followed until resolution of the complication prior to exiting the subject. Should a surgical complication occur during the second-eye surgery and result in implantation of a non-study lens, the subject will not be exited from the study; the first eye will continue to be followed per-protocol, although data may be analyzed separately, and the second eye will be followed for safety until resolution of the complication.

MEDICATIONS

Preoperative, operative and intraoperative medications should be used as is customary for each investigator and will be recorded on the CRF.

TYPE OF CLOSURE

Wound closure is left to the surgeon's discretion and will be recorded on the CRF.

ADDITIONAL OPERATIVE INFORMATION COLLECTED INCLUDES:

- Date of surgery
- Operative eye
- Lens power and serial number
- Lens placement
- Other surgical procedures
- Surgical technique according to protocol
- Product complaints
- Serious and/or device-related adverse events

10.7 POSTOPERATIVE PROCEDURES

Postoperatively, subjects will be examined according to the schedule in Section 10.2, Visit Schedule. Only the most recently operated eye will be evaluated at the 1-day and 1-week visits. Both eyes will be evaluated at the 1-month and 6-month visits.

Study technicians responsible for conducting all vision testing will be masked. Therefore, it is recommended that only the investigator/sub-investigator or other designated and trained clinician perform the biomicroscopic slit-lamp exams. To maintain consistency and masking throughout the study, it is recommended that a single individual (study technician or coordinator designated by the investigator) conduct all postoperative study-related vision testing, although a back-up person should also be designated and trained.

Note: Subjects are not to wear contact lenses postoperatively until after completion of this study. Wearing contact lenses may potentially cause corneal edema or topography changes that may influence the visual acuity results. During the study, if correction is required, spectacles should be prescribed.

A postoperative CRF will collect the following information, although not all data are required at every visit (see **Appendix A**):

MANIFEST REFRACTION AND REFRACTION ADJUSTMENTS (MASKED PROCEDURE)

Postoperative study manifest refractions are to be performed using the M&S System at a distance of 4.0 meters. Manifest refraction (MR) is to be performed using the Maximum Plus refraction method as detailed in **Appendix C**.

Because 4.0 meters is not optical infinity, refraction adjustments are necessary to ensure proper vision testing taking into account test distance and refraction distance.

Appendix D lists the refraction adjustments required for the various vision tests using the BCDVA refraction.

DISTANCE VISUAL ACUITY TESTING (MASKED PROCEDURE)

Distance visual acuity will be measured postoperatively under photopic lighting conditions (85 cd/m², 80–110 cd/m² acceptable) using the M&S System at a test distance of 4.0 meters. For eyes unable to achieve a postoperative BCDVA of Snellen 20/40 (i.e., LogMAR 0.3, number of letters correct 70), a reason must be specified. Instructions for using the M&S System are detailed in **Appendix E**, and for distance visual acuity in **Appendix F**.

The following distance visual acuity measurements are to be performed per the visit schedule in **Appendix A**:

Test	Test Distance	Illumination	Type of Testing	Refraction Adjustment
UCDVA	4 m	Photopic (85 cd/m ²)	Monocular Binocular	+0.25 D adjustment only
BCDVA	4 m	Photopic (85 cd/m ²)	Monocular Binocular	No adjustment; ETDRS Rx only

INTERMEDIATE VISUAL ACUITY (MASKED PROCEDURE)

Intermediate visual acuity (100% contrast) will be measured under photopic conditions (85 cd/m², 80-110 cd/m² acceptable) using the M&S System at a test distance of 66 cm. Instructions for using the M&S System are detailed in **Appendix E** and for intermediate testing in **Appendix G**.

The following intermediate visual acuity measurements are to be performed per the visit schedule in **Appendix A**:

Test	Test Distance	Illumination	Type of Testing	Refraction Adjustment
UCIVA	66 cm	Photopic (85 cd/m ²)	Monocular Binocular	No adjustment
DCIVA	66 cm	Photopic (85 cd/m ²)	Monocular Binocular	-0.25 D added to ETDRS sphere Rx

LOW CONTRAST INTERMEDIATE VISUAL ACUITY (10%) (MASKED PROCEDURE)

Low contrast (10% contrast) intermediate visual acuity will be measured under photopic conditions (85 cd/m², 80-110 cd/m² acceptable) using the M&S System at a test distance of 66 cm. Monocular best corrected intermediate visual acuity (BCIVA) at 66 cm under low contrast acuity (10%) conditions will be performed to determine the minimum amount of add necessary over the distance correction for the subject to achieve their best intermediate visual acuity similar to distance visual acuity in the primary eye (first eye to be implanted). Instructions for low contrast intermediate testing are detailed in **Appendix G**.

The following intermediate visual acuity measurements are to be performed per the visit schedule in **Appendix A**:

Test	Test Distance	Illumination	Type of Testing	Refraction Adjustment
DCIVA	66cm	Photopic (85 cd/m ²)	Monocular	-0.25 D added to ETDRS sphere Rx
BCIVA*	66 cm	Photopic (85 cd/m ²)	Monocular	-0.25 D added to ETDRS sphere Rx

* Intermediate visual acuity tested through distance correction with minimum add required to reach best corrected intermediate visual acuity.

NEAR VISUAL ACUITY (MASKED PROCEDURE)

Near visual acuity will be measured under photopic conditions (85 cd/m², 80-110 cd/m² acceptable) using the Good-Lite self-calibrating, retro-illuminated box with 100% contrast ETDRS near charts at a test distance of 40 cm.

Instructions for using the ETDRS near chart, including setting appropriate lighting conditions, and the visual acuity conversion chart between the number of ETDRS letters read and Snellen equivalents are provided in **Appendix H**.

The following near visual acuity measurements are to be performed per the visit schedule in **Appendix A**:

Test	Test Distance	Illumination	Type of Testing	Refraction Adjustment
UCNVA	40 cm	Photopic (85 cd/m ²)	Monocular Binocular	No adjustment
DCNVA	40 cm	Photopic (85 cd/m ²)	Monocular Binocular	-0.25 D added to ETDRS sphere Rx

DEPTH OF FOCUS TESTING (MASKED PROCEDURE)

Monocular, best corrected distance depth of focus testing will be performed at the 1-month visit on the first eye only for all subjects, and binocular best corrected distance depth of focus testing will be performed at the 6-month visit on all subjects.

Depth of focus testing will be performed under photopic conditions (85 cd/m², 80-110 cd/m² acceptable) using the M&S System at 4.0 meters with the ETDRS refraction in place (no adjustment necessary for test distance). The subject is to be defocused in -0.50 D increments with spherical minus lenses; at each defocus increment, a LogMAR measurement is obtained. Testing is to be conducted from +2.00 D through -4.00 D of defocus. Defocus curves will be generated for small (≤ 2.5 mm), medium (> 2.5 to < 4.0 mm), and large (≥ 4.0 mm) pupil sizes. Further instructions for defocus testing are detailed in **Appendix I**.

The following defocus curve measurements are to be performed per the visit schedule in **Appendix A**:

Test	Test Distance	Illumination	Type of Testing	Refraction Adjustment
Monocular Depth of Focus	4 m	Photopic (85 cd/m ²)	Monocular	No adjustment; ETDRS Rx only
Binocular Depth of Focus	4 m	Photopic (85 cd/m ²)	Binocular	No adjustment; ETDRS Rx only

TOLERANCE TO CYLINDER (MASKED PROCEDURE)

Binocular best corrected manifest cylinder defocus testing will be performed at the 1-month visit under photopic conditions (85 cd/m², 80-110 cd/m² acceptable) using the M&S System at 4.0 meters with the ETDRS refraction in place (no adjustment necessary for test distance). The subject is to be defocused in -0.50 D increments, from -0.50 D to -3.00 D of cylinder; at each cylinder defocus increment, a LogMAR measurement is obtained. Refer to **Appendix J** for further instructions.

PUPIL SIZE

Photopic, photopic with glare, mesopic and mesopic with glare pupil sizes will be measured postoperatively during the study. For consistency, the same method of measurement should be used throughout the study.

Photopic pupil size measurements are to be performed under the same lighting conditions at which photopic distance visual acuity is tested. Pupil sizes under the other lighting conditions will be measured during the contrast sensitivity testing procedures. Instructions for measuring pupil size are detailed in **Appendix K**.

DISTANCE CONTRAST SENSITIVITY TESTING (MASKED PROCEDURE)

Best corrected distance contrast sensitivity will be tested under mesopic, mesopic with glare, and photopic with glare conditions using the M&S System for sine-wave gratings at 1.5, 3.0, 6.0, 12.0 cycles per degree (cpd) (mesopic and mesopic with glare) and 3.0, 6.0, 12.0 and 18.0 (photopic with glare). **The test distance is 8 feet (2.5 meters)**. Best corrected distance contrast sensitivity is to be performed with a +0.12 D refractive adjustment to the sphere of the manifest refraction. Detailed instructions for contrast sensitivity testing are provided in **Appendix L**.

The following contrast sensitivity measurements are to be performed per the visit schedule in **Appendix A**:

Contrast Sensitivity Test	Test Distance	Spatial Frequency	Type of Testing	Refraction Adjustment
Mesopic (3 cd/m ²) without glare	2.5 m	1.5, 3, 6 and 12 cpd	Monocular Binocular	+0.12 D added to ETDRS sphere Rx
Mesopic (3 cd/m ²) with glare	2.5 m	1.5, 3, 6 and 12 cpd	Monocular Binocular	+0.12 D added to ETDRS sphere Rx
Photopic (85 cd/m ²) with glare	2.5 m	3, 6, 12 and 18 cpd	Monocular Binocular	+0.12 D added to ETDRS sphere Rx

BIOMICROSCOPIC SLIT-LAMP EXAM

A biomicroscopic slit-lamp exam must be performed at each postoperative visit to determine the presence or absence of any medical or lens findings, complications or adverse events. IOL decentration and tilt are to be determined subjectively. The center of the lens relative to the pupil can be used to determine IOL decentration, with the diffractive rings used as a guide to locate the center of the IOL. Note that the pupil center may not always be aligned with the visual axis of the eye; therefore, the investigator should consider deviations in pupil center from visual axis when reporting IOL decentration.

Findings of aqueous cells and flare, corneal edema, posterior capsule striae (wrinkles), posterior capsular opacification and IOL glistenings are to be rated using standardized grading scales of 0 to +4 (0 = none, +4 = severe) during the slit-lamp biomicroscopy. The specific grading scales are provided in **Appendix M**.

ND:YAG CAPSULOTOMY

If an Nd:YAG capsulotomy is necessary, it is recommended that the procedure be performed at least 1 week prior to a study exam; this is particularly important for the 6-month study visit, as this is the key study exam for evaluation of safety and effectiveness.

DILATED FUNDUS EXAM

A dilated fundus exam is to be performed at the 6-month visit to evaluate retinal status and fundus visualization.

INTRAOCULAR PRESSURE AND KERATOMETRY

Intraocular pressure (IOP) and keratometry are to be measured using the investigator's usual methods. It is recommended that the same methods be used for all study subjects at the site for the duration of the study.

OCULAR SYMPTOMS (NON-DIRECTED; SPONTANEOUS)

Subjective ocular symptoms are to be assessed at each postoperative visit by asking "Are you having any difficulties with your eyes/vision?" Subjects should not be prompted for specific responses; however, if a subject reports halos, night glare or starbursts, the level of severity should be determined (mild, moderate or severe).

MEDICATIONS

Postoperative ocular medications should be used as is customary for each investigator and recorded in the source document for each subject. Medications will be recorded on a medication log CRF as applicable.

ADVERSE EVENTS

Subjects should be assessed at each visit for occurrence of and/or change in status of any adverse events, particularly serious and/or device-related adverse events. See Section 11.0, Adverse Events, for further information.

QUESTIONNAIRES

Questionnaires will be administered at the 1-month and 6-month visits to collect information regarding spectacle usage, visual symptoms, visual quality and subject satisfaction. In order to minimize any effect the doctor-patient relationship may have on a subject's responses on the questionnaire, the study questionnaires will be

self-administered by the subjects. The questionnaires are to be administered at the start of the 1-month and 6-month study visits, prior to any visual acuity testing.

In addition, if a subject is seen at an Unscheduled visit due to an optical/visual symptom complaint, the PRO Visual Symptoms Questionnaire will be administered at that visit, as well as prior to any secondary surgical intervention for an optical/visual symptom complaint. If additional unscheduled visits and/or a secondary surgical intervention due to the same optical/visual symptom complaint occur within 2 weeks of each other, it is not necessary to complete the PRO Visual Symptoms Questionnaire a second time.

If the subject indicates in the PRO Visual Symptoms Questionnaire that they have visual symptoms or other problems with their vision that are bothersome enough to want the lenses removed and replaced, the investigator will document a determination for whether or not, in their opinion, the problem is related to the optical properties of the lens.

10.8 EXIT OF SUBJECTS

An Exit CRF will be completed for all subjects, either when they complete the study or if they exit early.

It is the responsibility of the investigator to provide complete follow-up data to AMO for each subject, and every attempt should be made to gather that complete follow-up data for all subjects enrolled, as missing data can have a negative effect on the study results. Patients who would be traveling, relocating or otherwise unavailable for postoperative follow-up visits should not be enrolled in this clinical study.

A subject will be considered a "screen failure" if he/she does not meet the eligibility criteria or if consent is withdrawn prior to randomization.

A subject will be considered "discontinued prior to treatment" if the subject is randomized but does not undergo surgery or receive a study lens for various reasons including: the planned implant being aborted due to surgical complications, the subject withdrawing consent prior to treatment or the subject died prior to treatment.

Subjects will be "discontinued" from the study if one study lens (if implanted unilaterally) or both study lenses (if implanted bilaterally) are removed or if the subject dies.

If a subject receives at least one study lens, he/she is to be followed according to the schedule in Table 2 (Section 10.2) for visit windows.

Subjects will be considered "lost-to-follow-up" from the study only if irretrievably lost for unavoidable reasons such as: subject moved/unable to locate, subject ill/unable to travel, subject uncooperative/refuses further study participation. In the event of subject

relocation, effort must be made by the investigator to secure follow-up information (i.e., slit-lamp findings and general visual acuity, etc.) from the subject's new physician.

If a subject is exited early from the study, the investigator must indicate the reason for study exit on the CRF. In the event of a lens removal or other serious adverse event, the subject may be exited from the study; however, effort must be made by the investigator to follow the subject until resolution of the adverse event before exiting the subject from the study.

Following study completion or early exit, subjects will be informed about which lens model they received. Additionally, all study subjects are to be instructed to undergo regular eye examinations at least yearly and also to return to their doctor if any eye complications are experienced.

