- Residual refractive error resulting in a secondary surgical intervention
- Retained lens material resulting in secondary surgical intervention

NOTE 1: Wound burps during the first week postoperatively, suture removal, planned blepharoplasty and Nd:YAG capsulotomy (for PCO) are not considered adverse events for this study.

NOTE 2: Raised IOP requiring treatment, cornea edema, and iritis will only be considered serious if persistent at the final study visit (120-180 days postoperative) or sight-threatening at the time of occurrence. Treatment merely to hasten the resolution of such conditions (and not intended to prevent permanent damage to the eye) will not be reported as serious adverse events.

Unanticipated Adverse Device Effect (UADE)/Unanticipated Serious Adverse Device Effect (USADE)

Any UADE (USA 21CFR 812.3(s)) or USADE (ISO 14155) is defined as any serious adverse effect on health or safety or any life-threatening problem or death caused by, or associated with, a device, if that effect, problem, or death was not previously identified in nature, severity, or degree of incidence in the investigational plan (i.e., this protocol), application (including a supplementary plan or application), or risk assessment, or any other unanticipated serious problem associated with a device that relates to the rights, safety, or welfare of subjects.

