11.5 ADVERSE EVENT FOLLOW-UP

For every adverse event, appropriate measures should be undertaken to treat and/or monitor the subject until resolution occurs. The subject's files are to include all pertinent medical data relating to the event including the subject's medical records, medical reports and/or judgments from colleagues or outside specialists who assisted in the treatment and follow-up of the subject. The investigator should keep AMO closely informed as to the outcome of serious and/or device-related adverse events, thereby allowing AMO to comply with the appropriate regulatory reporting requirements. A Detailed Adverse Event Update CRF should be completed each time the subject returns to the investigator or other specialist(s) for follow-up of serious and/or device-related adverse event until resolution of the event. Any subject who is to be exited from the study due to a serious and/or device-related adverse event should be followed until the outcome is determined prior to being exited from the study.

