20.1 ANALYSIS POPULATION

The safety population (SP) of all subjects implanted who have available data will be used for all analysis. No data imputation will be performed for missing data. For the monocular endpoints, the safety population will consist of first eyes implanted with a study IOL; for binocular endpoints, the safety population will consist of subjects implanted with the same IOL in both eyes. The primary analysis population will be the safety population (SP) for all endpoints.

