20.3 ADDITIONAL ENDPOINTS

For BCDVA, the frequency and proportion of eyes achieving each acuity line will be reported over time by IOL group. The proportion of investigational lens eyes achieving 20/40 or better at 6 months will be compared to the ISO SPE rate for posterior chamber IOLs (all first eyes) using a one-sided, exact test based on binomial distribution. The null hypothesis (based on the ISO guidance document) is that the proportion of investigational lens eyes achieving 20/40 or better BCDVA is greater than or equal to the ISO SPE values, and the alternative hypothesis is that the proportion of investigational lens eyes achieving 20/40 or better BCDVA is less than the ISO SPE values.

In addition, the mean LogMAR BCDVA will be compared between lens groups for first eyes using a non-inferiority method. The null hypothesis is that the mean difference (control minus investigational lens) between the control and investigational IOLs is ≤ -0.1 LogMAR (1 line) with the alternative hypothesis that the mean difference is > -0.1 LogMAR. A 90% confidence interval (CI) of a two-sample, two-sided, t-test will be used for evaluation.

For all other near endpoints, statistics similar to DCNVA described above will be used. In addition, the frequency and proportion of first eyes achieving each line will be reported over time by IOL group.

For intermediate endpoints, the mean LogMAR values will be analyzed similar to BCDVA described above. The frequency and proportion of first eyes achieving each line will also be reported over time by IOL group.

For defocus results, the defocus curve will be produced by IOL group. The diopters of defocus where the mean visual acuity 20/32 or better is achieved will be derived by visual inspection of the defocus curve.

For questionnaire data, including visual symptoms, the frequency and proportion of subjects with a given response will be reported by IOL group. For comparisons between IOL groups, Wilcoxon Rank-Sum test will be used for ordinal data, and Fisher's exact test will be used for categorical data. The null hypothesis is that there is no difference between responses, and the alternative hypothesis is that there is a difference between responses. Two-sided testing and alpha of 0.05 will be used to evaluate questionnaire data.

For contrast sensitivity data, descriptive analyses including mean, standard deviation, median, minimum, maximum and 90% confidence intervals will be presented by IOL group.

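### Protocol 10.8 allows exit after a serious adverse event without tying follow-up to month 6, so the available-data 20/40 rate can leave out first eyes with complications

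*Protocol*

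**What the plan says.** Protocol 10.8 contains three rules on follow-up.

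- General rule: "If a subject receives at least one study lens, he/she is to be followed according to the schedule in Table 2".
- Optional exit: "In the event of a lens removal or other serious adverse event, the subject may be exited from the study". The same sentence adds that "effort must be made by the investigator to follow the subject until resolution of the adverse event before exiting the subject from the study".
- Mandatory discontinuation: "if one study lens (if implanted unilaterally) or both study lenses (if implanted bilaterally) are removed or if the subject dies".

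Protocol 11.5 adds that a subject exited because of a serious or device-related event "should be followed until the outcome is determined prior to being exited from the study".

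On the analysis side, Protocol 20.3 states: "The proportion of investigational lens eyes achieving 20/40 or better at 6 months will be compared to the ISO SPE rate". SAP 7.2 repeats this. The test is one-sided and exact, and its null hypothesis is that the rate is at or above the ISO value. Protocol 20.1 restricts all analyses to implanted subjects with data and says: "No data imputation will be performed for missing data". SAP 2.1 takes the same position and presents whatever was collected before exit. SAP 3.1 counts discontinued and missing eyes. Neither document includes a sensitivity analysis for missing data or says how a first eye exited before month 6 enters the 20/40 proportion.

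**The concern.** The general rule and the optional exit in 10.8 do not fit together. The first keeps an implanted subject to month 6, and the second allows the subject to leave after a complication. The safeguard between them ends when the event resolves or its outcome is known, and either can happen well before the 6-month window.

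The analysis then uses only eyes with a 6-month value. If eyes that leave after a complication are more likely to be below 20/40 than eyes that stay, the reported proportion is too high. Because the null hypothesis is that the lens meets the ISO rate, losing failing eyes also makes rejection less likely, which is the favourable result for the lens. At stake is a named additional safety endpoint, assessed at the visit that Protocol 10.7 (Nd:YAG capsulotomy) calls the key exam for safety and effectiveness.

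**Working it through.** **Following one eye through the rules.** Suppose a first eye has a serious event in month 2 and permanent acuity loss is established in month 3.

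1. Under 11.5 the outcome is determined, so the condition for exit is met.
2. Under 10.8 the subject may then be exited.
3. No BCDVA is taken at 120 to 180 days.
4. Under 20.1 nothing is imputed, so the eye is in neither the numerator nor the denominator of the 6-month proportion.
5. SAP 2.1 presents the earlier data, but does not bring the eye into that proportion.

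If the sole study lens or both study lenses are removed, the exit at step 2 is required, not optional.

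**How many eyes can be missing.** Protocol 20.6 and SAP 8 plan 65 evaluable per group at 10% dropout: 65 / (1 − 0.10) = 72.2, rounded up to 73. The stated 73 is reproduced. That leaves 73 − 65 = 8 first eyes per group without 6-month data from all causes. Protocol 8 instead puts drop-out of implanted subjects at about 5%, or 73 × 0.05 = 3.65, about 4 eyes. Neither figure says how many would be exits after a serious event.

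**Effect on the reported rate.** Let k of 73 first eyes be exited below 20/40, with all others seen at month 6 and successful. The available-data rate is (73 − k)/(73 − k) = 100% for any k. With every eye counted it is (73 − k)/73.

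| k | Rate with every eye counted |
|---|---|
| 1 | 72/73 = 98.6% |
| 2 | 71/73 = 97.3% |
| 3 | 70/73 = 95.9% |
| 8 | 65/73 = 89.0% |

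Each eye is worth 1/73 = 1.4 percentage points.

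**Effect on the test.** The ISO rate is not in the documents, so a range of 90% to 99% is assumed. The BCDVA test has no alpha of its own, so the SAP 2.3 default of 0.05 is used. With X the number of failing eyes, the one-sided exact p-value is P(X ≥ k) for X ~ Binomial(73, 1 − ISO rate).

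| k | ISO 90% | 92.5% | 95% | 97% | 99% |
|---|---|---|---|---|---|
| 1 | 0.9995 | 0.997 | 0.976 | 0.892 | 0.520 |
| 2 | 0.996 | 0.977 | 0.886 | 0.647 | 0.166 |
| 3 | 0.981 | 0.918 | 0.713 | 0.375 | 0.037 |
| 8 | 0.448 | 0.180 | 0.029 | 0.0016 | <0.0001 |

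With one to three failing exits and no other failures, the conclusion changes only for three exits at an assumed 99%. If all eight planned losses were failing eyes, it would change at 95% and above.

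**Near the boundary.** At an assumed ISO rate of 92.5%, 9 failures in 65 eyes give p = 0.053 (not rejected). Adding one omitted failing eye makes it 10 in 66, with p = 0.025 (rejected). A single exit can decide the test there, but only if the observed count is already close to the limit.

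**The case against.** The strongest reply is that exit after a serious event is optional, and that the protocol pulls the other way several times. It sets the Table 2 rule, asks for every attempt at complete data, and asks for follow-up to resolution before exit. The endpoint is not primary. The primary safety endpoint is adverse event rates, and a serious event that leads to exit has already been recorded. SAP 3.1 makes the missing eyes visible. Most of this stands and limits the size of the point. It does not close the gap, because none of these provisions ties an exited subject to the 6-month visit, and counting missing eyes does not correct the proportion.

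Four stronger readings are tempting, and the documents do not support them.

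- *That the 6-month rate is in fact computed without the worst eyes.* Apart from death, the only exits that 10.8 requires of implanted subjects are for removal of the sole lens or of both lenses. Otherwise exit is a possibility of unknown frequency.
- *That rates of persistent raised IOP, corneal edema and iritis are biased downward in the same way.* Note 2 in 11.1 says these "will only be considered serious if persistent at the final study visit (120-180 days postoperative", but it goes on to include cases that threaten sight when they occur. Before the final visit these conditions are therefore not normally serious and do not trigger the exit option. A sight-threatening case already counts, and an unresolved one should still be under follow-up. What remains is narrow: an eye exited because of a different serious event has no final-visit assessment.
- *That every such exit is an eye likely to fail.* Serious events include non-ocular hospitalisation and second-eye events, which say little about first-eye acuity.
- *That exits should be taken from 65, giving 62/62 against 62/65 = 95.4%.* The 65 is already net of dropout, so this counts attrition twice. The base is the 73 implanted.

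**Conclusion.** The point holds in limited form. Section 10.8 is inconsistent about follow-up after a serious event or lens removal. Combined with an available-data analysis and no sensitivity analysis, it allows first eyes with complications to be left out of the 6-month 20/40 comparison. The bias is upward in the rate and towards not rejecting the null hypothesis, on the assumption that exited eyes do worse on average than those that stay.

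The illustrative size is 100% reported against 95.9% for three failing exits among 73. One to three exits would usually move the reported rate and leave the test result unchanged, unless the ISO rate is very high or the count is near the boundary. The number of exits and the ISO rate are not in the documents, so no changed conclusion is shown. The change is worth making because it is cheap, not because the endpoint is shown to fail.

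**What to change.** 1. **Protocol 10.8.** Reconcile the optional-exit sentence with the Table 2 rule, so that a serious adverse event or lens removal does not by itself end data collection. Subjects continue scheduled assessments (BCDVA, slit-lamp, adverse events) to the 6-month visit unless consent is withdrawn. Reconcile the mandatory-discontinuation sentence for lens removal to match. Protocol 19 already applies this principle after a study suspension, when treated subjects complete the visit schedule.
2. **Protocol 20.3 and SAP 7.2.** Keep the available-data analysis as the main one. Add a sensitivity analysis for first eyes with a serious event or lens removal and no 6-month BCDVA, counting them first as not achieving 20/40 and alternatively by their last available postoperative BCDVA. Cross-refer from Protocol 20.1 and SAP 2.1, which currently rule out any imputation.

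The substitution should not enter the main analysis. A last available value may come from the acute phase, or from a Snellen chart at an unscheduled visit (Protocol 10.9) and not from the study system, and could bias the rate downward. Once lens-removal eyes stay in data collection, the SAP should also say how a BCDVA measured after removal is treated.

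The cost is a few sentences in each document, a few extra scheduled visits, and a 20/40 rate that may read slightly less favourably.
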